6.4 Discontinuation/Withdrawal Procedures

N/A

7. METHODOLOGY**7.1 Survey Schedule**

The schedule of observations and assessments during the survey are summarised below.

Table 1. Schedule of Observations

	Day 0	Follow-up visit	Telephone contact if no follow up visit

Demography& Eligibility	X		
Treatment injections	X		
Adverse events		X	X

7.2 Survey Visits

7.2.1 *Baseline (Day 0, visit 1)*

All subjects attending the centre for their normal Dysport treatment will receive Dysport as decided by the treating physician, in accordance with the marketing authorisation. The following details will be recorded on the survey CRF:

- Centre number
- Subject number
- Subject initials,
- Demography
- Previous Toxin history
- Indication
- Dysport administration

7.2.2 *Follow-up visit*

Patients will then return for their normal follow up visit and an assessment of safety will be recorded on the CRF along with any AEs that have occurred since the last treatment.

- Collection of adverse events

7.2.3 *Telephone contact*

Contact will be made with the patient by telephone after planned normal follow-up visit, or if the patient is unavailable to visit. Patients will be asked about any AEs that they may have experienced since they received their Dysport treatment. These AEs will be recorded on the CRF.

7.2.4 *Survey Completion or Withdrawal*

N/A

8. SURVEY EVALUATIONS

8.1 Efficacy Endpoints and Evaluations

None

8.1.1 *Primary Efficacy Endpoint and Evaluations*

None

8.1.2 *Secondary Efficacy Endpoints and Evaluations*

None

8.2 Safety Endpoints and Evaluations

8.2.1 *Adverse Events*

AEs will be collected from the first treatment administration to the end of the follow-up period. AEs will be elicited by direct, non-leading questioning or by spontaneous reports. Further details for AE reporting can be found in Section 10.

9. SURVEY TREATMENTS

9.1 Survey Treatments Administered

Administration of Dysport will be supervised by the Investigator, or designee.

Survey medication

Chemical name:	Clostridium botulinum type A toxin-hemagglutinin complex
Survey Code:	Dysport
Dosage form:	Powder for dilution and injection
Strength:	500 units
Manufacturer:	Ipsen Biopharm Ltd., Wrexham, United Kingdom (UK)
Description:	Dysport is supplied as a white, lyophilized powder containing 500 units of Clostridium botulinum type A toxin-haemagglutinin complex, 125 µg human serum albumin, and 2.5 mg of lactose. The product will be reconstituted at the investigational sites with sterile physiologic saline for injection without preservative.

9.2 Subject Identification and Allocation to Survey Treatment

All subjects enrolled must be identifiable throughout the survey. The Investigator will maintain a list of subject numbers and names to enable records to be found at a later date if required. This record called Subject Identification Code List should be kept confidential at the survey centre.

The subject number will be allocated at baseline visit following the chronological order of the subject entry into the survey at a particular site. Subjects will be identified using a unique subject identification during the survey: site number + subject number. Subject number and site number will be noted in the CRF.

9.2.1 Randomisation

NA

9.2.2 Blinding, Emergency Envelopes and Breaking the Blind

NA

9.3 Survey Treatment Supply

The centre will purchase Dysport vials, each bearing a unique lot number, by their normal method. The Dysport is the commercially available material in the country.

Centres will prescribe Dysport according to their normal practice and in respect to the SmPC.

9.4 Compliance

NA

9.5 Survey Treatment Storage

Until dispensed to the patients, Dysport will be stored refrigerated, as is the custom at the hospital/practice.

9.6 Concomitant Medication/Therapy

NA

10. ADVERSE EVENT REPORTING

An AE is the development of an undesirable medical condition or the deterioration of a pre-existing medical condition following or during exposure to a pharmaceutical product, whether or not considered causally related to the product. An undesirable medical condition can be symptoms (e.g. nausea, chest pain), signs (e.g. tachycardia, enlarged liver) or the abnormal results of an investigation (e.g. laboratory findings, electrocardiogram). In clinical studies an AE can include an undesirable medical condition occurring at any time, including run-in or washout periods, even if no survey treatment has been administered.

This definition includes events occurring from the time of the subject receiving the first administration of Dysport until the end of the survey.

10.1 Disease Progression

NA

10.2 Categorisation of Adverse Events

10.2.1 Intensity Classification

AEs will be classified as mild, moderate or severe according to the following criteria:

- Mild: symptoms do not alter the subject's normal functioning
- Moderate: symptoms produce some degree of impairment to function, but are not hazardous, uncomfortable or embarrassing to the patient
- Severe: symptoms definitely hazardous to well-being, significant impairment of function or incapacitation.

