10.2.2 Causality Classification

The relationship of an AE to the Survey medication will be classified according to the following:

- Related: reports including good reasons and sufficient information (e.g. plausible time sequence, dose-response relationship, pharmacology, positive de-challenge and/or re-challenge) to assume a causal relationship with the Survey medication in the sense that it is plausible, conceivable or likely.
- Not related: reports including good reasons and sufficient information (e.g. implausible time sequence and/or attributable to concurrent disease or other drugs) to rule out a causal relationship with the Survey medication.

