10.4.2 Reporting Requirements

In this Post Marketing Survey only Related Serious Adverse Events will be reported immediately (within 24 hours) by Investigator to sponsor on the Clinical Study Serious Adverse Events forms. All other SAEs will be reported on the AE forms of the CRF.

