11.4.5 Safety Evaluation

All safety data will be displayed in the subject data listings. Analyses and summary tables will be based upon the safety population.

AEs will be coded according to the Medical Dictionary for Regulatory Activities (MedDRA) and will be classified by MedDRA preferred term and system organ class. AE listings will be presented by subject, system organ class and preferred term.

Incidence of all reported AEs/treatment emergent AEs (TEAE) and SAEs will be tabulated. In addition, summary tables will be presented by maximum intensity, drug relationship and AEs/TEAEs associated with premature withdrawal of survey medication.

A TEAE is defined as any AE that occurs during the active phase of the survey if:

it was not present prior to receiving the first dose of Survey medication, or

it was present prior to receiving the first dose of Survey medication but the intensity increased during the active phase of the survey, or

it was present prior to receiving the first dose of Survey medication, the intensity is the same but the drug relationship became related during the active phase of the survey.

Treatment emergent AEs will be flagged (*) in the AEs listings.

Concomitant medication will be coded by using WHO Drug Dictionary and will be summarised with the number and percentage of subjects receiving concomitant medication by drug class and preferred drug name.

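### The intensity grades in 10.2.1 leave one kind of adverse event without a grade and give another kind two grades; 10.2.2 also lacks a rule for events whose causality cannot be determined

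*Protocol*

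**What the plan says.** Protocol 10.2.1 sets a three-grade scale with no further category: "AEs will be classified as mild, moderate or severe according to the following criteria".

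- The lowest grade, Mild, is for events that leave usual functioning as it was.
- The middle grade, Moderate, is for events whose "symptoms produce some degree of impairment to function, but are not hazardous, uncomfortable or embarrassing to the patient".
- The highest grade, Severe, is met by definite hazard, by a significant loss of function, or by incapacity.

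Protocol 10.2.2 sets two causality classes. Both demand good grounds and enough information. For Related, these must allow the assessor "to assume a causal relationship with the Survey medication in the sense that it is plausible, conceivable or likely"; for Not related, they must allow the assessor "to rule out a causal relationship with the Survey medication". There is no third class and no default. Section 10.3 tells the investigator to obtain enough information to settle causality and to enter the assessment on the CRF. It does not say what to enter when that fails.

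Both scales are used in the analysis. Under 11.4.5, "summary tables will be presented by maximum intensity, drug relationship" and events tied to premature withdrawal. The same section's definition of a treatment-emergent event refers, for conditions already present before the first dose, to a rise in intensity or a change in drug relationship.

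**The concern.** Moderate appears to have been written with its qualifier the wrong way round. It takes in partial loss of function only if the patient feels neither discomfort nor embarrassment. Partial impairment that is also uncomfortable is not a contrived combination, yet it has no home on the scale. At the other end, Mild looks only at function while Severe can be met by hazard alone, so the two overlap.

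Adverse events are the survey's only endpoint (4.2.1, 4.2.2), and about 20 centres (6.1) will grade them. Without a usable definition, each site will choose the neighbouring grade it prefers or leave the field empty. Differences in the maximum-intensity table could then reflect site custom. The causality scale raises a similar problem on a smaller scale for the drug-relationship table.

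These are definitions that investigators apply when the data are entered. An analysis plan written afterwards cannot restore a judgement that had no definition at the time.

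**Working it through.** There is no planned figure to reproduce. The 500 subjects are justified by practicality alone (11.3), and no testing is planned (11.3.1). The check is therefore logical.

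**Intensity.** The three definitions use three attributes: impairment of function (none, some, significant including incapacitation), hazard (no, yes), and discomfort or embarrassment (no, yes). That gives 3 × 2 × 2 = 12 profiles. The rules as written are:

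- Mild if impairment is none.
- Moderate if impairment is some, hazard is no, and discomfort or embarrassment is no.
- Severe if hazard is yes or impairment is significant.

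| Impairment | Hazard | Uncomfortable or embarrassing | Grade(s) met |
|---|---|---|---|
| none | no | no | Mild |
| none | no | yes | Mild |
| none | yes | no | Mild and Severe |
| none | yes | yes | Mild and Severe |
| some | no | no | Moderate |
| some | no | yes | **none** |
| some | yes | no | Severe |
| some | yes | yes | Severe |
| significant | no | no | Severe |
| significant | no | yes | Severe |
| significant | yes | no | Severe |
| significant | yes | yes | Severe |

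Result: 9 profiles have exactly one grade, 1 has none and 2 have two (9 + 1 + 2 = 12). These are counts of logical cases, not of expected events.

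**Intensity after the change proposed below.** Mild becomes impairment none and hazard no. Moderate becomes impairment some and hazard no, whatever the discomfort. Severe is unchanged. The two double-graded profiles become Severe only, the ungraded profile becomes Moderate, and the other 9 keep their grade. All 12 then have exactly one grade.

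**Causality.** Cross whether information is sufficient (yes, no) with the conclusion reached (link can be assumed, link ruled out, undetermined): 2 × 3 = 6 cells. Related covers sufficient information with a link that can be assumed. Not related covers sufficient information with a link ruled out. The other 4 cells have no class: every cell with insufficient information, and the cell with sufficient information but no conclusion either way. The last of these should be rare, given how little Related asks for.

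**What cannot be computed.** If a share r of events is clearly related and a share u is undetermined, the reported related share lies between r and r + u, depending on the default each site adopts. The protocol supplies neither r nor u, so the width of that range is unknown.

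**The case against.** The best case for the plan has four parts.

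1. The opening of 10.2.1 obliges sites to assign one of three grades, and the function axis alone runs from unaltered through some impairment to significant impairment. A sensible investigator would grade uncomfortable partial impairment as Moderate. This is probably what sites would do, and it limits the practical effect. But it asks them to ignore an exclusion that the definition states outright, and it does not settle the overlap of Mild and Severe.

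2. On causality, 10.3 instructs the investigator to gather what is needed, 10.4.3 has the sponsor ask for a causality assessment missing from an initial SAE report, and the threshold for Related is low. This stands in part: the gap is narrowed. It is not closed, because even the low threshold presupposes sufficient information and no fallback is given.

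3. The survey is descriptive. Overall incidence of adverse events and of serious events, and the subject listings, do not depend on either scale. That stands. It does not extend fully to treatment-emergent events, since intensity and relationship both enter that definition for conditions present before treatment.

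4. A reader might infer that an undetermined serious event recorded as Not related loses 24-hour reporting, because 10.4.2 says "only Related Serious Adverse Events will be reported immediately". The documents do not support that as a flat statement. Section 10.4.1 requires all serious events within 24 hours whatever the suspected relationship, and 10.6 requires the same for fatal events with no causality condition. The outcome depends on how 10.4.1 and 10.4.2 are reconciled, which is a separate contradiction.

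**Conclusion.** The intensity scale in 10.2.1 is defective as written. It is neither exhaustive nor mutually exclusive: 1 of 12 attribute profiles has no grade and 2 of 12 have two. This rests on reading the definitions literally and on treating hazard as the same yes/no attribute in all three grades.

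The causality gap in 10.2.2 is real but secondary, because 10.3 and the low bar for Related reduce how often it should arise.

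Two stronger readings go too far. One is that the planned tables will be wrong by some stated amount. With no event rates in the protocol, neither the number of events nor any shift in a percentage can be given, and wrong grading is a likely consequence of forced choice rather than something the text establishes. The other is that all uncomfortable events are ungradable. Those with no impairment are Mild if not hazardous, and those with significant impairment or hazard meet Severe.

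The correction is worth making before data collection, because it bears on how the only endpoint is recorded. It affects no test, error rate or sample size.

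**What to change.** In 10.2.1:

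- Mild: keep the present criterion and add that the symptoms are not hazardous.
- Moderate: some impairment of function, not hazardous; the symptoms may be uncomfortable or embarrassing.
- Severe: unchanged. Use one hazard threshold throughout, so that not hazardous in Mild and Moderate is the exact complement of the hazard criterion in Severe.

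In 10.2.2, state one rule for all sites on how an event is recorded when the information sought under 10.3 cannot be obtained. One option is a not-assessable category shown as its own row in the drug-relationship table, with a sensitivity count that adds it to Related. Counting such events as Related outright would also close the gap, but it hides how many are undetermined. Either is defensible if it is fixed in advance.

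Carry both definitions onto the adverse event page of the CRF, which is not shown in the document. Separately, reconcile 10.4.1 with 10.4.2 so that the reporting route for a serious event of undetermined causality is unambiguous.

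The cost is a few sentences in the protocol, matching CRF text and, if the extra category is adopted, one more row in a table. No additional data need to be collected.

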10.2.2 Causality Classification

The relationship of an AE to the Survey medication will be classified according to the following:

- Related: reports including good reasons and sufficient information (e.g. plausible time sequence, dose-response relationship, pharmacology, positive de-challenge and/or re-challenge) to assume a causal relationship with the Survey medication in the sense that it is plausible, conceivable or likely.
- Not related: reports including good reasons and sufficient information (e.g. implausible time sequence and/or attributable to concurrent disease or other drugs) to rule out a causal relationship with the Survey medication.

10.2.3 Assessment of expectedness

NA

10.2.4 Laboratory Test Abnormalities

NA

10.2.5 Abnormal Physical Examination Findings

NA

10.2.6 Other Investigation Abnormal Findings

NA

10.3 Recording and Follow-up of Adverse Events

At each visit the patient should be asked a non-leading question such as: "Do you feel different in any way since starting the new treatment/the last assessment?"

All observed or volunteered AEs, regardless of treatment group or suspected causal relationship to Survey medication, will be recorded on the AE page(s) of the CRF. Events involving drug reactions, accidents, illnesses with onset during the treatment phase of the survey, or exacerbation's of pre-existing illnesses should be recorded.

AEs already recorded and designated as ‘continuing’ should be reviewed at each subsequent assessment.

For all AEs, the Investigator must pursue and obtain information adequate both to determine the outcome of the AE and to assess whether it meets the criteria for classification as a SAE requiring immediate notification to the Sponsor or its designated representative. For all AEs, sufficient information should be obtained by the Investigator to determine the causality of the AE (i.e., Survey medication or other illness). The Investigator is required to assess causality and record that assessment on the CRF. Follow-up of the AE, after the date of therapy discontinuation, is required if the AE or its sequelae persist. Follow-up is required until the event or its sequelae resolve or stabilise at a level acceptable to the Investigator and the Sponsor’s clinical monitor or his/her designated representative.

10.4 Serious Adverse Events

10.4.1 Definitions

All SAEs (as defined below) regardless of treatment group or suspected relationship to Survey medication must be reported immediately (within 24 hours of the Investigator’s knowledge of the event) to the pharmacovigilance contact specified at the beginning of this protocol. If the immediate report is submitted by telephone, this must be followed by detailed written reports using the SAE report form.

A SAE is any AE occurring at any dose that:

1. results in death;
2. is life threatening, that is any event that places the patient at immediate risk of death from the reaction as it occurred. It does not include a reaction that, had it occurred in a more severe form, might have caused death;
3. results in in-patient hospitalisation or prolongation of existing hospitalisation, excluding admission for social or administrative reasons (see further);
4. results in a persistent or significant disability/incapacity, where disability is a substantial disruption of a person's ability to conduct normal life functions;
5. results in congenital anomaly/birth defect in the offspring of a patient who received the Survey medication;
6. is an important medical event that may not result in death, be life-threatening, or require hospitalisation when, based upon appropriate medical judgement, may jeopardise the patient and may require medical or surgical intervention to prevent one of the outcomes listed in this definition. Examples of such medical events include allergic bronchospasm requiring intensive treatment in an emergency room or at home, blood dyscrasias or convulsions that do not result in in-patient hospitalisation, or the development of drug dependency or drug abuse.

Regardless of the above criteria, any additional AE that the Sponsor or an Investigator considers serious should be immediately reported to the Sponsor and included in the corporate SAEs database system.

- **Hospitalisation** is defined as any in-patient admission (even if less than 24 hours). For chronic or long-term in-patients, in-patient admission also includes transfer within the hospital to an acute/intensive care in-patient unit.
- **Prolongation of hospitalisation** is defined as any extension of an in-patient hospitalisation beyond the stay anticipated/required in relation to the original reason for the initial admission, **as determined by the Investigator or treating physician**. For protocol-specified hospitalisation in clinical trials, prolongation is defined as any extension beyond the length of stay described in the protocol. Prolongation in the absence of a precipitating, treatment-emergent, clinical AE (i.e., not associated with the development of a new AE or worsening of a pre-existing condition) may meet criteria for "seriousness" but is not an adverse experience and thus is not patient to immediate reporting to the Sponsor.
- Pre-planned or elective treatments/surgical procedures should be noted in the patient's screening documentation. Hospitalisation for a pre-planned or elective treatment/surgical procedure should not be reported as an SAE unless there are complications or sequelae which meet the criteria for seriousness described above.

10.4.2 Reporting Requirements

In this Post Marketing Survey only Related Serious Adverse Events will be reported immediately (within 24 hours) by Investigator to sponsor on the Clinical Study Serious Adverse Events forms. All other SAEs will be reported on the AE forms of the CRF.

10.4.3 Mandatory Information for Reporting Related SAE

The following information is the minimum that must be provided to the Sponsor pharmacovigilance contact within 24 hours for each SAE:

- Trial number
- Centre number
- Subject number
- AE
- Investigator's name and contact details

The additional information included in the SAE form must be provided to the Sponsor or representative as soon as it is available. Upon receipt of the initial report, the Sponsor will ask for the Investigator's causality assessment if it was not provided with the initial report.

The Investigator should report a diagnosis or a syndrome rather than individual signs or symptoms. The Investigator should also try to separate a primary AE considered as the foremost untoward medical occurrence from secondary AEs which occurred as complications.

10.5 Pregnancy

Pregnancy is not a criterion of seriousness. However, any unintended pregnancy occurring during treatment with the survey drug should be reported in the same timelines as an SAE, using the pregnancy reporting form. The

investigator/monitoring physician will be instructed by the sponsor in the tracking of the pregnancy outcome (a special form to obtain the information required will be sent to the monitoring physician).

A female patient must be instructed to stop taking the survey drug and immediately inform the investigator if she becomes pregnant during the survey. The investigator should report all pregnancies to the sponsor within 24 hours of becoming aware of them. The investigator should counsel the patient; discuss the risks of continuing with the pregnancy and the possible effects on the foetus. Monitoring of the subject should continue until conclusion of the pregnancy.

